#### **E. Potential Scientific Problems:**

*Potential for dosing of intervention to be specific to participant.* Standardizing the number of visits for all participants allows us to control the intervention dose for the PAB intervention. We acknowledge that not all patients will necessarily require the same number and frequency of visits to achieve an optimal response to the intervention. However, our pilot study data and previous literature in other populations support the 10 visits that will be used in the current intervention. We expect our exploratory analysis will identify key determinants of responsiveness, which then can be used to help better dose the PAB intervention to individual patients in future studies of clinical implementation.

*Missing data.* All participants with outcome measurements will be included in the intent-to-treat analysis. Although the protocol encourages participants to be fully compliant with the assigned intervention and testing sessions, no one will be dropped from follow-up measurements for lack of compliance. We will make every effort to prevent missed intervention sessions and test visits. Figures examining the pattern of missing data will be created to provide insight into the mechanism of the missingness and guide the analysis in an appropriate manner. If the

data are missing completely at random, analyses of complete cases will provide unbiased parameter estimates; provision for missing data due to dropout has been accounted for in the sample size justification. If the data are missing at random, valid analyses may still be performed using a likelihood-based analysis of all available data, still generating unbiased parameter estimates.

## **F. Data Analysis Plan:**

The primary outcome for this study is average number of steps taken per day, as measured by accelerometer-based wearable sensors (activPAL) over a 7-day period at the end of the intervention. This time point is chosen for clinical relevance to establish efficacy of the intervention. Sustainability will be tested as a secondary outcome, by assessing steps taken per day six months after conclusion of the intervention period. Other secondary outcomes include time spent in standing/walking activities and physical function measures. Preliminary descriptive and graphical analyses (including boxplots, scatterplots, profile plots of change over time) will be used for data cleaning, data visualization, and assessing statistical assumptions.

***Primary Analysis (Aim 1):*** The primary analysis will be an intent-to-treat comparison of the differences between the study groups (PAB and CTL) in the change average daily step count from PREOP to POST2 (primary endpoint). Statistical inference will be based on the estimated coefficient for the group variable using an analysis of covariance (ANCOVA) model with change in average daily step count from PREOP to POST2 as the response variable. Additional covariates include the stratification variables (PREOP physical activity and age) to improve the precision of the estimate. The conclusion about group differences will be made based on this single statistical test to control the type I error rate at 0.05. A similar between-group analysis will be performed on the change in daily step count from PREOP to POST3 (6-month effect post-intervention). A sensitivity analysis will be done to evaluate whether conclusions would differ when other covariates are added to the model (e.g., demographics, anthropometrics, comorbidities, psychosocial factors).

***Secondary Analyses (Aims 1 & 2):*** Differences between study groups in the secondary outcomes of 1) time spent in standing/walking activity (activPAL) and 2) physical function (performance-based and self-reported outcomes), from PREOP to POST2 will be analyzed as described above for the primary analysis. All outcomes will also be analyzed at POST3 to evaluate the long-term sustainability of the PAB intervention. We anticipate that the secondary outcomes will be correlated with the primary outcome, and would interpret the results from the secondary analysis as reinforcing the findings in the primary outcome. Failure to observe consistency between primary and secondary outcomes will be interpreted as evidence that the effects of the PAB intervention are not clear, and that further study is necessary to resolve inconsistencies. This approach reduces the risk of false-positive conclusions resulting from multiple statistical tests.

***Exploratory Analysis (Exploratory Aim):*** The exploratory analysis will delineate the mechanisms underlying responsiveness to the PAB intervention by using multiple linear regression to identify key predictors of average daily step count from PREOP to POST2 in the PAB group. We will use the approach of fitting all possible models to identify the most parsimonious model predictive of the primary outcome of changes in steps per day across the intervention period. Candidate predictor variables will be those with theoretical evidence of predicting physical activity, including: PREOP steps per day, demographics (age, sex, education level), anthropometrics (height, weight, BMI), and comorbidities (Functional Comorbidity Assessment). In addition, we will focus specifically on physical activity-related psychosocial factors (depression, exercise self-efficacy, exercise readiness to change, social support, and fear of falling). The set of candidate predictor variables will be assessed for collinearity (and any collinearity reduced to the extent possible) before beginning model selection procedures. With  $k$  predictor variables, there are  $2^k$  possible regression models. Each of the  $2^k$  models will be fit and both 1) the adjusted  $R^2$  and 2) Mallows'  $C_p$  statistic will be generated for each model. A plot of Mallows'  $C_p$  vs  $p+1$  (where  $p$  = the number of model parameters) will be used to identify parsimonious candidate models according to Hocking's criterion. The best candidate models will be compared using their statistical properties as well as subject knowledge expertise and practical considerations (e.g. an objective variable may be preferred over a subjective variable). A final model will be selected from the candidate models. We hypothesize that baseline average steps per day at PREOP and all included psychosocial factors will be significant determinants of intervention responsiveness. The results of this exploratory aim will provide evidence for clinicians in determining the prognosis of patients in terms of likely physical activity improvement from the PAB intervention. We hypothesize that the PAB intervention will effectively increase physical activity, as measured in average steps per day. Whether that hypothesis is proven or not, the exploratory aim will add to the current body of rehabilitation knowledge by identifying key predictors of future activity based on baseline variables.

***Qualitative Analysis (Exploratory Aim):*** Pragmatic qualitative analysis will be used to analyze data from the semi-structured interviews. Savin-Baden outlined three steps to pragmatic qualitative research: (1) visually familiarize yourself with the data by reading the transcripts, then identify primary categories, (2) generate conclusions, and

(3) check the results. The 14 domains of the Theoretical Domains Framework (TDF) will be used as a priori codes to classify the barriers and facilitators discussed by participants. The 14 domains in the TDF are: knowledge; skills; social/professional role and identity; beliefs about capabilities; optimism; beliefs about consequences; reinforcement; intentions; goals; memory, attention, and decisions processes; environmental context and resources; social influences; emotion; and behavioral regulation. The TDF domains will be used to as “primary categories” (i.e. a priori codes) to capture participants’ responses to barriers and facilitators of physical activity (step 1 in pragmatic qualitative analysis). The researcher will then read through the coded data as well as the data that was not coded to generate conclusions and construct themes related to perceived barriers and facilitators to physical activity and changes throughout the PAB program (step 2). Finally, the themes and raw data supporting each theme will be reviewed by the researcher with attention to accurate representation of participants’ perception of barriers and facilitators (step 3). To enhance rigor we will consider procedures to promote credibility, consistency, and transferability. First, to ensure credibility we will *triangulate* between data sources (interviewers notes, transcripts, and interdisciplinary discussion). Second, to enhance consistency, the researcher who is coding will keep an *audit trail* of all decisions related to coding, interpretation, and constructed themes. Third, we will randomly select up to 20 participants from the PAB group to ensure *maximal variation* in PAB group experience, and the experience of potential barriers and facilitators to physical activity.

Data analysis will be conducted with de-identified data on the Anschutz Medical Campus.

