## Study Protocol

### I. Hypotheses and Specific Aims:

The primary objective of this randomized controlled trial is to determine efficacy of physical activity behavior-change telerehabilitation on improving physical activity after total knee arthroplasty (TKA).

**Aim 1:** To determine if PAB (Physical Activity Behavior-Change) intervention results in improved physical activity after TKA compared to the control group (CTL). Physical activity will be measured using accelerometer-based wearable sensors and self-reported daily activity (Life-Space Assessment).

**Hypothesis 1.1:** The PAB group will have greater increases in accelerometer-assessed daily step count (primary outcome) and percent time engaged in standing & walking activity than the CTL group from PREOP to POST2 (primary endpoint), and group differences will persist at POST3.

**Hypothesis 1.2:** The PAB group will have greater improvements in Life-Space Assessment scores than the CTL group from PREOP to POST2 (primary endpoint), and group differences will persist at POST3.

**Aim 2:** To determine if PAB intervention results in better physical function after TKA compared to the CTL group. Physical function will be measured with standardized performance-based (30-Second Chair-Stand Test, Timed Up-and-Go, Six-Minute Walk Test) and self-report (Western Ontario and McMaster Universities Osteoarthritis Index [WOMAC] and Veterans RAND 12-Item Health Survey [VR-12]) measures.

**Hypothesis 2:** The PAB group will have greater improvements in all functional outcomes compared to the CTL group at POST2 and POST3 test points, with outcomes meeting clinically meaningful thresholds.

**Exploratory Aim:** To identify predictors underlying responsiveness to PAB rehabilitation (i.e., change in average daily step count) from PREOP to POST2 in the PAB group.

**Hypothesis 3:** We expect preoperative daily step count and physical activity-related psychosocial factors (self-efficacy, stage of change, social support, fear of falling) will be significant determinants of intervention responsiveness, in addition to key demographic, anthropometric, and comorbidity determinants.

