#### **G. Summarize Knowledge to be Gained:**

This study is an essential step for providing foundational evidence to support the effectiveness of a telerehabilitation approach aimed to increase physical activity in patients with TKA. The ultimate goal of this research line is to 1) develop and refine methods for implementing findings of the current study into clinical rehabilitation practice and 2) effectively disseminate these intervention methods to clinical institutions, both nationally and internationally. We will work with the Denver GRECC to develop strategies for operational partnerships both locally and nationally through Home Based Primary Care programs and through connections with other GRECC Associate Directors for Clinical Programs. In addition, [name] has developed strong working collaborations with the Center for Research in Implementation Science and Prevention (CRISP) at the University of Colorado Denver to facilitate additional strategies for rapid transition to implementation strategies immediately upon conclusion of the proposed investigation.

*Personalized Rehabilitation to Optimize Utilization.* Current rehabilitation guidelines after TKA are generalized based on population expectations. However, there is high individual variability within the population of Veterans undergoing TKA and thus, we expect variable responses to rehabilitation. By identifying the key predictors of responsiveness to intervention, we expect the results of our study to lead to methods for individually tailored approaches to personalize rehabilitation practices, which will optimize Veteran outcomes and lower overall costs.

*Application of Findings to Other VA Populations.* Future investigations could apply the proposed PAB rehabilitation to other populations with chronic physical activity deficits. We expect our findings to be generalizable to a variety of populations of Veterans who are routinely seen for orthopedic surgeries and other medical conditions. We chose to initially focus on TKA because of the high utilization of TKA, the great need to improve physical activity in these Veterans, and the ability to capitalize on the “teachable moment” of elective TKA surgery.

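### Predictors of step change in the PAB arm alone are read as determinants of response to PAB, which one arm cannot show

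*Combined protocol and SAP*

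**What the plan says.** Section I (Hypotheses and Specific Aims) sets the exploratory aim: "To identify predictors underlying responsiveness to PAB rehabilitation (i.e., change in average daily step count) from PREOP to POST2 in the PAB group". Response is therefore the raw change, and only PAB participants count.

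Section IV.F (Data Analysis Plan), Exploratory Analysis, carries this out by "using multiple linear regression to identify key predictors of average daily step count from PREOP to POST2 in the PAB group", with all-subsets selection among baseline variables. It attaches three readings to the result:

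- Mechanism: "The exploratory analysis will delineate the mechanisms underlying responsiveness to the PAB intervention".
- Determinants: "We hypothesize that baseline average steps per day at PREOP and all included psychosocial factors will be significant determinants of intervention responsiveness".
- Attribution to PAB: evidence for clinicians in "determining the prognosis of patients in terms of likely physical activity improvement from the PAB intervention".

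Two later sections build on this. Section IV.E: "We expect our exploratory analysis will identify key determinants of responsiveness, which then can be used to help better dose the PAB intervention". Section IV.G: "By identifying the key predictors of responsiveness to intervention, we expect the results of our study to lead to methods for individually tailored approaches".

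The only place where such variables enter a two-arm model is the primary analysis in section IV.F: "A sensitivity analysis will be done to evaluate whether conclusions would differ when other covariates are added to the model". There they are main-effect covariates. The Statistical Analysis Plan says that exploratory analyses followed the primary method, a mixed model with an arm-by-time term. It does not mention the PAB-only regression, and no section plans an arm-by-predictor term.

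**The concern.** Who gains steps among people given PAB is a question one arm can answer. Who gains more because of PAB is a question about a difference between arms, and it needs the control (CTL) arm.

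PREOP is two weeks before surgery and POST2 is the end of the intervention. The change between them contains the effect of the knee replacement, the conventional visits and the PAB sessions. Age, BMI, comorbidity, depression and fear of falling could each plausibly affect recovery whatever the telerehabilitation content. In the PAB arm alone, such a prognostic factor cannot be told apart from a factor that modifies the PAB effect.

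What is at stake is the use made of the result. If a general recovery factor is reported as a determinant of response to PAB, later work on dosing or tailoring PAB would select on a variable that says nothing about who benefits from it.

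**Working it through.** **The plan's own figures.** Section IV.B states 80.7% power for a two-sided 5% t-test with 40 per group and d = 0.64. The noncentral t distribution gives 80.70%, so it reproduces. It concerns the main group comparison. No power or precision is stated for the exploratory aim.

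**Raw change is not all PAB effect.** In the PAB pilot (section III) the PAB group gained 7067 − 5456 = 1611 steps/day and controls gained 5613 − 5250 = 363. The between-arm difference is 1611 − 363 = 1248, and 363/1611 = 23% of the raw change also occurred without PAB. That pilot began as outpatient therapy was ending, so the share is not an estimate for PREOP to POST2.

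**Simulation set-up.**

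- From the documents: SDs s1 = 2230 (pre-operative) and s2 = 2633 (month 3) from the Total column of Table 1; 40 per arm analysed, or 50 with no dropout.
- Assumed, because the documents give none: PREOP–POST2 correlation r, and the covariate's correlation with the residual (its partial correlation with outcome given PREOP steps).
- Outcome: POST2 = b × PREOP + arm effect + residual, with b = r × s2/s1 and residual SD = s2 × √(1 − r²).
- PAB-only model: change on PREOP + covariate.
- Two-arm model: change on PREOP + arm + covariate + arm × covariate.
- 20,000 runs per setting at 40 per arm; 8,000 at 50.

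**A. Purely prognostic covariate** (same correlation in both arms, constant PAB effect, r = 0.6). Proportion of trials significant at 5%:

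| Partial correlation | PAB-only, n = 40 | PAB-only, n = 50 | Interaction, n = 40 per arm |
|---|---|---|---|
| 0.2 | 23.1% | 28.4% | about 5% |
| 0.3 | 47.0% | 56.4% | about 5% |
| 0.4 | 73.1% | 83.3% | about 5% |
| 0.5 | 91.6% | 96.5% | about 5% |

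The interaction column ranged from 4.7% to 5.2%.

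**B. True effect modifier** (correlation 0.4 under PAB, 0 in control; r from 0.4 to 0.8). The PAB-only test is significant in 73.0–73.6% of trials, the same rate as for the prognostic factor at 0.4. This follows by construction, since the PAB-arm data are generated identically, and that is the point: the PAB arm holds no information that separates the two cases. The interaction test gives 42.4–43.3% here against about 5% in A.

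**C. A modifier the PAB arm cannot show** (slope 0 under PAB, −0.64 SD per SD in control; simpler model without PREOP). The PAB-only test is significant in about 5% of trials. The interaction test is significant in 78% (40 per arm) or 87% (50 per arm).

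**Precision of the interaction in B.** The true interaction is 0.4 × 2633 × √(1 − r²): 0.4 × 2633 × 0.917 = 965 steps/day per SD of predictor at r = 0.4, and 0.4 × 2633 × 0.6 = 632 at r = 0.8. The mean 95% confidence interval half-width falls from 1072 to 701 over the same range, so it exceeds the true value throughout. On a standardised scale, 80% power needs a slope difference of (1.960 + 0.842) × √(2/40) = 0.63 SD per SD.

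**Multiplicity.** For five non-modifying factors tested singly, the chance of at least one significant interaction is 1 − 0.95⁵ = 22.6%; simulation gave 21.6–23.0%.

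**PREOP steps as a predictor.** The correlation of baseline with change is (r × s_post − s_pre)/SD_change, where SD_change = √(s_pre² + s_post² − 2 × r × s_pre × s_post). With pilot control SDs 1544 and 2388 it runs from −0.34 at r = 0.3 to +0.50 at r = 0.9. With pilot PAB SDs 3003 and 3677 it runs from −0.48 to +0.19. PREOP steps can therefore correlate with change in an arm that receives no PAB, partly through regression to the mean.

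**The case against.** The strongest reply is that much of the text is prognostic. Section I defines responsiveness operationally as step change in the PAB group. Section IV.F speaks of prognosis and closes by promising predictors of later activity. Read that way, a single arm is enough. This stands for those sentences, and the PAB-only model can be kept for them. It does not cover the mechanism and determinant claims, or the attribution of improvement to PAB.

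Second, the aim is exploratory and the intended uses are hedged and lie in future work. That limits the weight of the point. It excuses imprecision, but not reporting a different quantity from the one named.

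Third, the simulated percentages depend on assumed correlations, on SDs from an earlier trial's ActiGraph subset (this trial uses activPAL), and on one covariate tested at 5%. The plan instead screens 13 named candidates (1 + 3 + 3 + 1 + 5) by adjusted R² and Mallows' Cp, and that selection was not simulated. All of this is fair. The figures illustrate the problem and are not the plan's error rates.

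Fourth, the interaction analysis is weak at this sample size. That is true, and is why it should yield interval estimates and not significance claims.

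Finally, the SAP may have dropped the PAB-only regression. Its status is unclear, but the SAP's arm-by-time model does not test modification by baseline factors either.

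**Conclusion.** The concern holds. The exploratory analysis can describe which PAB recipients gain steps. It cannot identify determinants of response to PAB, and no other planned analysis does so. At assumed partial correlations of 0.2 to 0.5, a factor with no bearing on the PAB effect would be flagged in roughly a quarter to nine-tenths of trials with 40 in the arm, against about 5% for an arm-by-predictor test. These percentages rest on the assumed correlations and a one-covariate model; the failure to separate the two kinds of factor does not. The primary comparison is untouched, so the weight is minor to moderate. It should still be corrected, because sections IV.E and IV.G carry the reading into dosing and tailoring.

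**What to change.** - **Analysis.** In section IV.F, estimate arm-by-predictor interactions for change to POST2 using both arms, adjusted for PREOP steps. Take predictors one at a time or from a short prespecified list, and report estimates with confidence intervals, labelled exploratory. For PREOP steps, the arm-by-PREOP term also removes regression to the mean common to both arms.
- **Wording.** Keep the PAB-only all-subsets model solely as a prognostic model among PAB recipients. Remove the responsiveness, determinant and mechanism language for it in sections I (including Hypothesis 3), IV.E, IV.F and IV.G.
- **SAP.** Add a paragraph stating which exploratory analysis applies, labelled post hoc if results are already known.

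The cost is text in four protocol sections and one SAP paragraph. The control arm already supplies the baseline measures and step outcome, so no new data are needed. The drawback is the low precision and the multiplicity shown above. If the sponsor declines the interaction estimates, the wording change alone removes the unsupported inference.

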## CONSORT Flow Diagram

[figure not shown]

Figure 3. Anticipated CONSORT Flow Diagram

Inclusion criteria: 50-85 years of age at enrollment, Veteran, and planned unilateral primary TKA.

Exclusion criteria: severe non-surgical limb pain (pain >5/10 on non-surgical limb with walking); unstable orthopedic, neurologic, or pulmonary conditions that limit physical function; unstable cardiac condition; uncontrolled hypertension; uncontrolled diabetes; acute systemic infection; active cancer treatment; or recent stroke (within 2 years).

Statistical power was estimated using variability estimates from our pilot data collection, where the change in physical activity (steps/day) was assessed in 42 participants (21 receiving intervention, 21 attention control) following TKA. The observed SD of percent change after 3 months of intervention for the pilot sample was 42%, with an effect size of  $d=0.64$ . This effect size equates to a detectable difference of 1,611 steps per day between groups. Based on this expected group difference, a 2-sample, 2-sided t-test at the 5% level with 80 patients (40 per group) would have 80.7% power to detect a group difference. We will enroll 100 participants (50 per group) to allow for a ~20% loss to follow-up. Previous clinical trials in our laboratory, for patients with TKA, have resulted in dropout rates of 4.9% and 6.5% at 3 months post-op and 8.2% and 15.2% at 12 months. Therefore, we are conservatively estimating a dropout rate of 20% at 9 months.

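### Hypothesis 3 tests PREOP steps against a zero slope in a PAB-only change-score model, where no relation with true gain would not give a zero slope

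*Combined protocol and SAP*

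**What the plan says.** The Exploratory Aim in protocol section I defines responsiveness as "change in average daily step count) from PREOP to POST2 in the PAB group". Hypothesis 3 in the same section begins "We expect preoperative daily step count and physical activity-related psychosocial factors" and expects these to be significant determinants of it. Section IV.F (Exploratory Analysis) uses the same response, seeking "the most parsimonious model predictive of the primary outcome of changes in steps per day across the intervention period", and puts baseline steps first among the candidates: "PREOP steps per day, demographics (age, sex, education level), anthropometrics (height, weight, BMI), and comorbidities". Selection is by all-subsets regression using adjusted R² and Mallows' Cp. The section then repeats the hypothesis: "We hypothesize that baseline average steps per day at PREOP and all included psychosocial factors will be significant determinants of intervention responsiveness".

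No direction, alpha or null slope is given for this test. Neither the protocol nor the SAP mentions regression to the mean, a reliability correction, or a control-arm contrast for this aim. The SAP says only that exploratory analyses follow the mixed-model method of the primary outcome; it describes no predictor regression.

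**The concern.** PREOP steps is part of the response it is asked to explain. A participant whose PREOP week happened to be unusually quiet will have a low predictor value and, on average, an inflated gain, even if the true gain is the same for everyone. A significant negative coefficient is therefore expected more often than 5% of the time when baseline activity has no bearing on response.

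The exploratory label does not make this harmless. Section IV.F says the results will inform clinicians' prognosis, section IV.E expects them to help dose the intervention in future studies, and section IV.G expects them to support individually tailored rehabilitation. An artefact could be carried forward as a finding that less active patients respond better to PAB. The same bias could also hide a real association in the opposite direction.

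**Working it through.** **Sample size.** The protocol gives no power figure for this aim. Its only one is for the primary comparison: "a 2-sample, 2-sided t-test at the 5% level with 80 patients (40 per group) would have 80.7% power to detect a group difference". With d = 0.64, df = 78 and noncentrality 0.64 × √20 = 2.86, the noncentral t gives 80.7%, so that figure reproduces. It supplies the 40 evaluable PAB participants used here. A two-sided 5% test is assumed for the exploratory aim.

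**Expected slope.** Let s1 and s2 be the SDs of PREOP and POST2 steps, and R the reliability of the 7-day PREOP count (the share of its variance that is true activity). Suppose true gain is unrelated to true baseline and the two weeks' errors are independent. Then:
- Cov(PREOP, POST2) = R·s1², so the slope of POST2 on PREOP is R.
- The slope of (POST2 − PREOP) on PREOP is R − 1. This is the no-relation value; zero is correct only if R = 1.
- SD of change = √(s1² + s2² − 2R·s1²).
- Correlation of change with PREOP = (R − 1)·s1 / SD of change. With s1 = s2 this is −√((1 − R)/2).

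**SDs.** Pilot PAB arm (section III): 3003 before, 3677 after. Earlier trial, Table 1, total column: 2230 pre-operative, 2633 at month 3. Equal SDs are a third, assumed case. R is not in the documents; 0.9 to 0.6 is an assumed range.

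**Worked example, pilot SDs.** s1² + s2² = 9,018,009 + 13,520,329 = 22,538,338.
- R = 0.9: SD of change = √(22,538,338 − 16,232,416) = 2,511; correlation = −0.1 × 3003 / 2511 = −0.120.
- R = 0.6: SD of change = √(22,538,338 − 10,821,611) = 3,423; correlation = −0.4 × 3003 / 3423 = −0.351.

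**Chance of p < 0.05 at n = 40** (simulated under bivariate normality), with the expected correlation in brackets:

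| SDs | R = 0.9 | R = 0.8 | R = 0.7 | R = 0.6 |
|---|---|---|---|---|
| Pilot PAB | 11% (−0.120) | 26% (−0.211) | 44% (−0.286) | 62% (−0.351) |
| Table 1 total | 13% (−0.130) | 29% (−0.224) | 48% (−0.301) | 66% (−0.366) |
| Equal | 29% (−0.224) | 52% (−0.316) | 71% (−0.387) | 84% (−0.447) |

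All are false rejections, and the rates are higher with 50 completers.

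**Effect of the model search.** With 12 candidates (11 of them noise), minimum-Cp selection, n = 40, equal SDs and a PREOP–POST2 correlation of 0.7, PREOP was selected and significant in 72% of 300 simulated trials, against 71% when it is the only predictor. The search does not remove the problem.

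**The case against.** **The rate may be low.** At a fixed PREOP–POST2 correlation of 0.7 or 0.8, the pilot PAB SDs give rejection in only 17% or 5% of samples. This is correct, but it is mostly not the no-relation case. If reliability equals that correlation, the slope of true POST2 on true PREOP is 3677/3003 = 1.22, so true gain rises by about 0.22 step per baseline step and the artefact is masking a real association. The documents' other figures do not settle the rate. Reading 1,611/0.64 = 2,517 as the SD of change, the pilot PAB SDs imply a correlation of 0.73 and 12% rejection, while the Table 1 totals imply 0.47 and 72%. The pilot baseline was also post-operative, so its correlation may not carry over. A reader might infer that PREOP steps will come out significant in most trials; that is not established.

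**The psychosocial predictors.** A reader might also infer that predictors correlated with activity, such as self-efficacy, carry the same artefact in models that omit PREOP. They do not. A score related to true activity is unrelated to that week's noise, and in simulation under the null it was significant in about 5% of samples.

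**Forcing PREOP into every model.** This looks like a natural repair, but error-prone PREOP under-adjusts for true activity. Null predictors correlated with activity then became significant in 9% to 54% of samples (reliability 0.5 to 0.8, correlation with true activity 0.3 to 0.7).

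**Exploratory and prognostic purpose.** For forecasting, baseline is a legitimate predictor and regression to the mean belongs in a correct forecast. This stands. It limits the point to the reading of the coefficient as a determinant of responsiveness.

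**Conclusion.** The point holds for one coefficient and one reading of it. A significant PREOP slope in the PAB-only change-score model is not evidence that baseline activity determines response, because the test uses the wrong null value. The false rejection rate is at least double the nominal 5% in every setting in the table, running from about 11% to 84%. Where it falls depends on the 7-day reliability and the SD ratio. Reliability is assumed here and absent from the documents; the SDs are borrowed from a pilot and an earlier trial. The calculation also assumes normality and independent errors between weeks. No claim is made that the finding is bound to appear, or that the other predictors are contaminated. The primary between-group test is not affected, since there the inference is on group and PREOP is only a covariate.

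**What to change.** In Hypothesis 3 and in section IV.F (Exploratory Analysis), remove PREOP steps from the hypothesised determinants of responsiveness. Add a sentence that its coefficient in the PAB-only change-score model is descriptive or prognostic and is not evidence of differential response. PREOP may stay among the candidates for prediction, but should not be forced into every model.

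If the sponsor wants to know whether baseline activity modifies the intervention effect, prespecify the arm-by-PREOP interaction with POST2 steps as the response, using both arms. Regression to the mean acts equally in the two arms and cancels in that contrast; in simulation its type I error was about 5%.

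The change is one of wording and uses data already collected. The SAP is written in the past tense, but reporting and interpretation can still be corrected. The cost is that one hypothesised exploratory finding is dropped, or is replaced by a test with limited power: with equal arms, the standard error of a difference in slopes is about √2 times that of a single-arm slope.
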